3.7 CRITERIA FOR REMOVAL FROM PROTOCOL THERAPY AND OFF STUDY CRITERIA

Regardless of reason for removal from study therapy, patients will be asked to have follow up safety visit within 90 days after the last vaccine. Patients who refuse to return for this visit will be asked to review any safety concerns by phone within this time period.

3.7.1 Criteria for removal from protocol therapy

- Completion of protocol therapy.
- Clinical or radiographic progression of disease Patients with serological progression alone will remain on treatment at the discretion of the PI.
- Unacceptable Toxicity as defined as any serious adverse event that is unexpected relative to the known safety profile of the investigational agents in the opinion of the investigator or as described in sections [3.1.1](#) and [3.3](#)
- Participant requests to be withdrawn from active therapy
- Investigator discretion
- Positive pregnancy test

Also see section [3.3](#)

3.7.2 Off-Study Criteria

- PI decides to end study
- Participant requests to be withdrawn from study. Reasons for withdrawal will be documented.
- Noncompliance with protocol guidelines (patient removed at discretion of Principal Investigator)
- Death
- Screen failure

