6 DATA COLLECTION AND EVALUATION

6.1 DATA COLLECTION

Data will be entered in C3D. The PI will be responsible for overseeing entry of data into an in-house password protected electronic system and ensuring data accuracy, consistency and timeliness. The principal investigator, associate investigators/research nurses and/or a contracted data manager will assist with the data management efforts. All data obtained during the conduct of the protocol will be kept in secure network drives or in approved alternative sites that comply with NIH security standards. Primary and final analyzed data will have identifiers so that research data can be attributed to an individual human subject participant.

All adverse events, including clinically significant abnormal findings on laboratory evaluations, regardless of severity, will be followed until return to baseline or stabilization of event. Patients will be followed for adverse events for a minimum of 30 days after removal from study treatment or until off-study, whichever comes first.

An abnormal laboratory value will be recorded in the database as an AE only if the laboratory abnormality is characterized by any of the following:

- Results in discontinuation from the study
- Is associated with clinical signs or symptoms
- Requires treatment or any other therapeutic intervention
- Is associated with death or another serious adverse event, including hospitalization.
- Is judged by the Investigator to be of significant clinical impact
- If any abnormal laboratory result is considered clinically significant, the investigator will provide details about the action taken with respect to the test drug and about the patient's outcome.

End of study procedures: Data will be stored according to HHS, FDA regulations, and NIH Intramural Records Retention Schedule as applicable.

Loss or destruction of data: Should we become aware that a major breach in our plan to protect subject confidentiality and trial data has occurred, the IRB will be notified.

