8.4.3.4 Overall Survival

OS will be evaluated by dose level and overall using Kaplan-Meier methods. OS will be defined as the time from the date of first treatment to the date of death (any cause). Subjects who are alive at the end of follow up will be censored at the last known date alive.

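### Removal for noncompliance takes a subject off study, where section 6.1 ends adverse-event follow-up, in conflict with its own rule on following events and with the safety visit in section 3.7

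*Combined protocol and SAP*

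**What the plan says.** All references are to the combined protocol and SAP.

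- **Section 3.7.2 (off study):** one criterion is "Noncompliance with protocol guidelines (patient removed at discretion of Principal Investigator". Section 3.7.1 lists the reasons for leaving therapy separately, and section 3.7.3 treats the two as distinct statuses, each notified to the registration office. The definition of non-compliance in section 7.1.9 concerns NIH policy, IRB and regulatory requirements. It does not describe a subject who misses visits.
- **Section 6.1 (duration):** "Patients will be followed for adverse events for a minimum of 30 days after removal from study treatment", and then "or until off-study, whichever comes first".
- **Section 6.1 (resolution):** all adverse events, "regardless of severity, will be followed until return to baseline or stabilization of event".
- **Section 3.7 (opening paragraph):** "Regardless of reason for removal from study therapy, patients will be asked to have follow up safety visit within 90 days after the last vaccine". Those who refuse to come back are asked to go over safety concerns by phone in the same period.
- **Section 3.5, footnotes l and m:** survival calls begin once a subject finishes or leaves study therapy. A patient unable to return for the 90-day visit is phoned about adverse events.
- **Sections 8.3 and 8.4.4:** one treatment is enough to make a subject evaluable for toxicity and safety.
- **Section 8.4.3.4:** "Subjects who are alive at the end of follow up will be censored at the last known date alive".

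**The concern.** Treatment-emergent adverse events and SAEs are primary endpoints (section 1.1.4). A subject who has had one injection counts in the denominator for them. If the investigator then takes that subject off study for noncompliance, section 6.1 read literally stops the collection of events, while two other rules say that it goes on. Staff handling such a case cannot tell which rule governs, and the one that stops collection is the easiest to apply.

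What is at stake is direction as much as size. A truncated record can only leave events out. If the reasons for removal are unrelated to the subject's condition, some information is lost but no bias follows. If they are related to toxicity or decline, the safety summary and the survival curve both err on the favourable side. Section 3.7.2 has no category for loss to follow-up, so noncompliance is the nearest subject-level entry for someone who simply stops attending. Attendance is itself a protocol requirement (section 2.1.1.13).

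**Working it through.** The plan gives no figure on this point, so there is none to reproduce. The check is mainly a comparison of rules.

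**1. The rules side by side**, for a treated subject taken off therapy and off study for noncompliance on the same day:

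| Rule | What it requires |
|---|---|
| 6.1, duration | Follow-up stops at off-study |
| 6.1, resolution | Each event is followed until back to baseline or stable |
| 3.7, opening | Visit or phone review within 90 days of last vaccine, whatever the reason for leaving therapy |
| 3.5, footnote m | Phone contact about events if the patient cannot return |
| 3.5, footnote l | Survival calls after leaving therapy; silent on off-study |

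The first row contradicts the second. It also conflicts with the third and fourth, which are timed from the last vaccine. No text says which prevails.

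**2. Guaranteed adverse-event follow-up under the duration rule.** Let d be the days from removal from treatment to off-study. The guaranteed follow-up is min(30, d):
- d = 0 gives 0 days
- d = 10 gives 10 days
- d = 30 or more gives 30 days

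The stated minimum is therefore not a minimum.

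**3. Survival contacts at risk.** Footnote l plans calls every 3 months for 12 months, every 6 months for 24 months, and every 12 months for 24 months. That is 12 + 24 + 24 = 60 months and about 12/3 + 24/6 + 24/12 = 4 + 4 + 2 = 10 calls. This is the most that could be lost for one subject, if off-study is taken to end them.

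**4. Effect of one hidden death on 12-month survival.** Inputs: 10 subjects at the MTD (section 3.1.2). Assumed: 5 of the 10 die within 12 months, so true survival is 50%; one of the five is censored before death and that death is never learned of; there is no other censoring. Four deaths are then observed.
- Censored before the other four deaths: (8/9)(7/8)(6/7)(5/6) = 5/9 = 55.6%, which is +5.6 points.
- Censored after the other four deaths: (9/10)(8/9)(7/8)(6/7) = 6/10 = 60.0%, which is +10 points.

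Other orderings fall between these. If the death does come to light and is entered, the shift is zero.

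**The case against.** The case on the other side is substantial.

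- **Safeguards exist.** A treated subject taken off study has also left therapy, so the opening of section 3.7 arguably covers that subject. Footnotes l and m state no off-study stop. Section 7.3 requires SAEs to be reported to the sponsor by time since dosing, and section 7.2.1 requires reports of deaths other than from progressive disease. A reader might infer that safety follow-up is simply cut off and serious events are lost. The documents do not support that. What remains is that the reporting duties are not active contact, and that no provision says it continues after off-study.
- **Illness as noncompliance is an inference.** A reader might conclude that the sickest subjects are the ones removed. No text says so. Section 3.3 allows delay for unrelated acute illness, section 3.7.1 lists progression, toxicity and investigator discretion as reasons to leave therapy only, and removal under section 3.7.2 is discretionary. Equally, illness-related absence is not exempted, and the delay rule does not cover toxicity or decline from the cancer.
- **OS is not censored on the off-study date.** Section 8.4.3.4 uses the date the subject was last known to be alive. The gap arises only if contact ends.
- **One removal does not lose 10% of the safety set.** One in 10 is 10%, but the subject stays in the set with all data up to removal. Only later observation is at risk.
- **The dose decision is largely protected.** It rests on a short window after the first dose (3 weeks in section 3.1.1, 1 week in section 8.4.4). Only a removal inside that window, counted as free of DLT, would matter. As an illustration, with five of six subjects observed, the chance of seeing two or more DLTs falls from 0.345 to 0.263 at an assumed true rate of 20%, and from 0.642 to 0.532 at 33%. The documents give no rate of such removals, so this shows direction and not an expected effect.

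**Conclusion.** The conflict is real and lies in stated rules, not in missing detail. The duration rule in section 6.1 can reduce adverse-event follow-up to nothing for a subject removed as noncompliant, while section 6.1's resolution rule and section 3.7 call for it to continue. The status of the survival calls after off-study is unstated.

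A favourable bias is conditional. It requires that removals are related to toxicity or decline and that the later events are not learned of by another route. Under the assumptions shown, one hidden death shifts 12-month survival by 5.6 to 10 points, so 10 points is a ceiling. No expected effect can be derived.

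The consequence is modest. The study is small, its analyses are descriptive (section 8.4.1), and survival is a preliminary secondary endpoint (section 8.4.3). The wording should still be reconciled, because adverse events are primary and the correction is cheap.

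**What to change.** Reconcile sections 3.7, 3.7.2 and 6.1 as follows.

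1. In section 6.1, limit the off-study cut-off to death or withdrawal of consent from the study. Deleting the clause outright would not work, because it would carry required follow-up past both of those.
2. In section 3.7.2, state that removal for noncompliance does not end data collection. The safety contact within 90 days, adverse-event follow-up and the telephone vital-status contacts in footnote l of section 3.5 all continue.
3. Say what noncompliance means for this criterion.

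Screen failures receive no vaccine and are not affected. If follow-up is also meant to stop when the investigator closes the whole study, section 6.1 can say so separately.

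The cost is a few sentences and a few more call attempts. The contacts are already planned, and no dose or treatment rule changes.

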3.7.3 Off Protocol Therapy and Off-Study Procedure

Authorized staff must notify Central Registration Office (CRO) when a subject is taken off protocol therapy and when a subject is taken off-study. A Participant Status Updates Form from the web site (<http://home.ccr.cancer.gov/intra/eligibility/welcome.htm>) main page must be completed and sent via encrypted email to: NCI Central Registration Office [contact].

4 CONCOMITANT MEDICATIONS/MEASURES

Subjects must inform the investigators of the current or planned use or all other medications during the study (including prescription medications, vitamins, herbal and nutritional supplements, and over-the-counter medications).

For the administration of ETBX vaccines, antiemetics, stool softeners, and antidiarrheal agents may be administered as required, but are not anticipated to be needed and should not be used prophylactically on the first cycle. The selection of the specific antiemetic regimen is at the discretion of the treating physician. Antiemetic regimens will not include steroids.

Other supportive care with blood components, antibiotics, analgesics, general medical therapy, etc., will be delivered as required. Any patients taking antibiotics for infection must complete that course of therapy and be free of evidence of further infection before receiving any dose of vaccine. Use of prophylactic antibiotics is allowed.

Concurrent systemic corticosteroid use (daily or every other day for continued use > 14 days) should be avoided within 28 days before the first planned dose of ETBX vaccines. Use of physiologic doses of systemic steroids, inhaled steroids, nasal sprays, and topical creams for small body areas is allowed.

Symptomatic anemia should be treated with appropriate red blood cell or erythropoietin support.

Thrombocytopenia should be treated conservatively. In the absence of bleeding or a planned invasive procedure, platelet transfusions should be given for a platelet count below 10,000/mm³. If invasive procedures are planned or the patient develops bleeding, platelet transfusions should be administered in accordance with the standard of practice, usually maintaining a platelet count of > 50,000/mm³.

4.1 CONCURRENT MEDICATIONS/INTERVENTIONS

4.1.1 Anticancer Therapy

If a subject requires additional systemic anticancer treatment with the exception of treatments described in section 3.1 then study treatment must be discontinued. Local intervention is discouraged unless medically unavoidable. Subjects receiving local intervention (*e.g.*, palliative radiation) are allowed to continue to receive study treatment at the investigator's discretion.

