Target lesions. All measurable lesions up to a maximum of 2 lesions per organ and 5 lesions in total, representative of all involved organs, should be identified as target lesions and recorded and measured at baseline. Target lesions should be selected on the basis of their size (those with the longest diameter), be representative of all involved organs, but in addition should be those that lend themselves to reproducible and repeated measurements. It may be the case that, on occasion, the largest lesion does not lend itself to reproducible measurement in which circumstance the next largest lesion which can be measured reproducibly should be selected. A sum of the diameters (longest for non-nodal lesions, short axis for nodal lesions) for all target lesions will be calculated and reported as the baseline sum diameters. If lymph nodes are to be included in the sum, then only the short axis is added into the sum. The baseline sum diameters will be used as reference to further characterize any objective tumor regression in the measurable dimension of the disease.

Non-target lesions. All other lesions (or sites of disease) including any measurable lesions above the 5 target lesions should be identified as non-target lesions and should be recorded at baseline. Measurements of these lesions are not required, but the presence, absence, or in rare cases unequivocal progression of each should be noted throughout follow-up.

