6.3.3 Methods for Evaluation of Measurable Disease

All measurements should be taken and recorded in metric notation using a ruler or calipers. All baseline evaluations should be performed as closely as possible to the beginning of treatment and never more than 4 weeks before the beginning of the treatment.

The same method of assessment and the same technique should be used to characterize each identified and reported lesion at baseline and during follow-up. Imaging-based evaluation is preferred to evaluation by clinical examination unless the lesion(s) being followed cannot be imaged but are assessable by clinical exam. The same mode of assessment (e.g., CT) used to identify/evaluate lesions at baseline should be used throughout the course of the study unless subject safety necessitates a change (e.g., allergic reaction to contrast media).

Clinical lesions: Clinical lesions will only be considered measurable when they are superficial (e.g., skin nodules and palpable lymph nodes) and ≥ 10 mm diameter as assessed using calipers (e.g., skin nodules). In the case of skin lesions, documentation by color photography, including a ruler to estimate the size of the lesion, is recommended.

Chest x-ray: Lesions on chest x-ray are acceptable as measurable lesions when they are clearly defined and surrounded by aerated lung. However, CT is preferable.

Conventional CT and MRI: This guideline has defined measurability of lesions on CT scan based on the assumption that CT slice thickness is 5 mm or less. If CT scans have slice thickness greater than 5 mm, the minimum size for a measurable lesion should be twice the slice thickness. MRI is also acceptable in certain situations (e.g. for body scans).

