6.3.5 Target Response

Percentage change in target lesion size will be evaluated by the following formulae:

1. When determining complete response or partial response:

$$[(\text{Post value} - \text{Baseline value})/\text{Baseline value}] \times 100$$

2. When determining progressive disease:

$$[(\text{Post value} - \text{Smallest value since treatment started})/(\text{Smallest value since treatment started})] \times 100$$

Target response will be classified according to the RECIST Version 1.1 Target Lesion Response Criteria in [Table 5](#).

Table 5: RECIST Target Response Criteria

Target Response Criteria	Definition
Complete Response (CR)	Disappearance of all target lesions. Any pathological lymph nodes (whether target or non-target) must have reduction in short axis to < 10 mm.
Partial Response (PR)	At least a 30% decrease in the sum of diameters of target lesions, taking as reference the baseline sum diameters.
Stable Disease (SD)	Neither sufficient shrinkage to qualify for PR nor sufficient increase to qualify for PD, taking as reference the smallest sum diameters while on study.
Progressive Disease (PD)	At least a 20% increase in the sum of diameters of target lesions, taking as reference the smallest sum diameters while on study (this includes the baseline sum if that is the smallest on study). In addition to the relative increase of 20%, the sum must also demonstrate an absolute increase of 5 mm. (Note: the appearance of one or more lesions is also considered progression).

Non-target response will be classified according to the RECIST Version 1.1 Non-Target Lesion Response Criteria in [Table 6](#).

Table 6: RECIST Non-Target Response Criteria

Non-Target Response Criteria	Definition
CR	Disappearance of all non-target lesions and normalization of tumor marker level. All lymph nodes must be non-pathological in size (< 10 mm short axis).
Non-CR / Non-PD	Persistence of one or more non-target lesion(s) and/or maintenance of tumor marker level above the normal limits.
PD	Unequivocal progression of existing non-target lesions. (Note: the appearance of one or more new lesions is also considered progression).

Overall response will be classified according to the RECIST Version 1.1 Overall Response Criteria in [Table 7](#).

Table 7: RECIST Overall Response Criteria

Target Lesions	Non-Target Lesions	New Lesions	Overall Response
CR	CR	No	CR
CR	Non-CR / Non-PD	No	PR
CR	Not Evaluated	No	PR
PR	Non-PD or not all evaluated	No	PR

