8.4.3.1 Objective Tumor Response and Disease Control Rate

The percentage of subjects that achieve an objective confirmed complete or partial overall tumor response using RECIST Version 1.1 will be evaluated by dose level and overall enrollment. If anti-tumor responses are observed, the 95% confidence interval of the response rate will be evaluated.

Disease control (confirmed response or SD lasting for at least 6 months) will be analyzed in a similar manner.

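### The response criteria make no exception for a target lesion treated locally on study, so the effect of permitted local therapy can be scored as vaccine response or disease control

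*Combined protocol and SAP*

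**What the plan says.** **Local therapy.** Section 4.1.1 sets a limit: "Local intervention is discouraged unless medically unavoidable". It then lets the subject stay on vaccine: "Subjects receiving local intervention (*e.g.*, palliative radiation) are allowed to continue to receive study treatment at the investigator's discretion". Palliative radiation is the only example it gives.

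**Which lesions are measured.** Under 6.3.2, "Target lesions should be selected on the basis of their size (those with the longest diameter), be representative of all involved organs". The diameters "for all target lesions will be calculated and reported as the baseline sum diameters". Section 6.3.3 adds: "The same method of assessment and the same technique should be used to characterize each identified and reported lesion at baseline and during follow-up".

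**How response is scored.** Table 5 in 6.3.5 defines PR as "At least a 30% decrease in the sum of diameters of target lesions, taking as reference the baseline sum diameters". CR requires all target lesions to disappear. PD requires a 20% and 5 mm rise from the smallest sum. None of these definitions refers to the cause of a change.

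**How response is analysed.** Section 8.4.3.1 states: "The percentage of subjects that achieve an objective confirmed complete or partial overall tumor response using RECIST Version 1.1 will be evaluated". Disease control means a confirmed response, or SD lasting at least 6 months. Section 8.4.3.3 counts progression or death as the PFS event and censors at the last date known to be progression-free.

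Sections 6.3.1 to 6.3.7, 8.3 and 8.4.3.1 to 8.4.3.3 say nothing about a lesion irradiated or removed on study. They do not drop it from the sum, make the subject inevaluable, count the intervention as an event, or censor at it.

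**The concern.** ORR, DCR, duration of response and PFS are meant to give a first look at vaccine activity. Followed literally, the criteria let the effect of another treatment enter these figures. A subject whose largest lesion is irradiated or removed can be classified as a responder or as having disease control on the strength of that procedure. Confirmation gives no protection, because such a lesion is normally still small or absent at the next scan. The fall in the treated lesion can also offset growth in the others, so that progression is missed or called late.

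The setting makes a single case matter. There is no control arm, at most 10 subjects contribute at the MTD, and 8.4.8 rules out tabulating individual participant data, so a reader of the results could not identify the case. In the earlier single-vaccine trial (1.2.6.3), the tumour outcome reported is 3 stable-disease events. Against that background, one PR produced by local therapy would stand out.

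**Working it through.** **Inputs from the plan.** Section 8.2 gives 6 subjects for dose evaluation plus 4 in expansion: 6 + 4 = 10 at the MTD, as stated. The most that can be treated is 12 + 4 = 16. Adding 16 screen failures gives 32, also as stated. The thresholds are those of Table 5. Lesion sizes below are assumed for illustration, because the documents give none.

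**When a treated lesion alone produces PR.** Section 6.3.5 uses (post − baseline)/baseline × 100. If the other target lesions are unchanged, PR follows when

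(treated lesion's share of the baseline sum) × (its fractional shrinkage) ≥ 0.30.

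- Share 0.60 (60 + 40 mm, the 60 mm lesion irradiated to 30 mm): 0.60 × 0.50 = 0.30. The sum goes from 100 to 70 mm, −30%: PR.
- Share 0.50: shrinkage of 0.30/0.50 = 60% is needed.
- Sole target lesion: 30% shrinkage is enough.
- Lesion removed: a 30% share is enough.

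**Scoring with and without the treated lesion.** Assumed target lesions are 50 + 30 + 20 mm (sum 100 mm), with the 50 mm lesion treated. The untreated lesions start at 50 mm in total.

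| Course | All target lesions | Scored as written | Untreated lesions | Untreated alone |
|---|---|---|---|---|
| Irradiated to 20 mm, others unchanged | 70 mm, −30% | PR | 50 mm, 0% | SD |
| Removed, others unchanged | 50 mm, −50% | PR | 50 mm, 0% | SD |
| Irradiated to 25 mm, others grow 20% | 85 mm, −15% | SD | 60 mm, +20%, +10 mm | PD |
| Removed, others grow 20% | 60 mm, −40% | PR | 60 mm, +20%, +10 mm | PD |

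In the last row, 60 mm becomes the new smallest sum. PD on target lesions then needs 60 × 1.20 = 72 mm, by which point the untreated lesions have grown 72/50 − 1 = 44%. The masking depends on timing. If the removed lesion is first scanned with the others unchanged (sum 50 mm), later growth to 60 mm is +20% and +10 mm from that nadir, and PD is called correctly.

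**Effect on ORR.** Exact (Clopper-Pearson) 95% intervals were used. For 0/n the upper limit is 1 − 0.025^(1/n). For 1/n the lower limit is 1 − 0.975^(1/n), and the upper limit is the matching beta quantile.

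| Denominator | No response | One response |
|---|---|---|
| 10 at the MTD | 0% (0 to 30.8%) | 10% (0.3 to 44.5%) |
| 16 treated | 0% (0 to 20.6%) | 6.3% (0.2 to 30.2%) |

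Both denominators are ceilings. Section 8.3 requires measurable disease for response evaluation, while 2.1.1.5 admits non-measurable and surgically resected disease. With 8 evaluable, for example, one case is worth 1/8 = 12.5 points.

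**The case against.** **Silence is not a rule.** A reader might infer that the plan expressly keeps treated lesions in the sum. It does not. Retention follows from the wording that covers all target lesions and from the lack of any exception. Section 6.3.4 adopts RECIST 1.1 in summary, and the guideline itself is not in the documents, so what it may say on treated lesions cannot be relied on either way. What stands is that the criteria written out here give the assessor no instruction. Table 7 has an inevaluable category for target lesions that are not all evaluated, but no text assigns a treated lesion to it, and an irradiated lesion can still be measured.

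**Existing limits.** Local intervention is discouraged. Clinical progression ends protocol therapy under 3.7.1, and an investigator may judge that the need for palliation is progression. New lesions or non-target PD give overall PD whatever the sum does. These limits reduce the exposure without closing it, because 4.1.1 does not class the need for local therapy as progression and allows vaccine to continue.

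**Palliative radiation often means bone.** A reader might infer that any palliative radiation can produce a PR. Section 6.3.2 classes bone lesions as non-measurable, so bone radiation cannot change the target sum. The problem concerns non-bone target lesions, and 4.1.1 is not confined to bone. Removal is a plausible local intervention, but 4.1.1 does not name it.

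**Small consequence.** Sections 8.4.1 and 8.4.3 describe efficacy as exploratory and preliminary, with no test or decision rule. This is correct, and it limits the weight of the point. A descriptive rate should still be attributable to the treatment it describes.

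**PFS should be censored at local therapy.** This is also tempting. The need for palliation may signal impending progression, so censoring there may be informative and could flatter PFS. Following subjects to progression regardless of local therapy, as 8.4.3.3 reads, is a legitimate approach.

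**Conclusion.** The gap is real and specific. Applied as written, the criteria can score shrinkage or removal of a non-bone target lesion by permitted local therapy as confirmed PR or CR, or as disease control. They can also hide or delay PD in untreated lesions.

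One case adds 10 percentage points to ORR if all 10 subjects at the MTD are response-evaluable, more if fewer are, and about 6 points if all 16 treated subjects are. It would be wrong to treat 10 points as a fixed cost per case, or to conclude that such cases will occur, because the documents give no frequency for local therapy. The lesion sizes are assumptions. The threshold relation between share and shrinkage follows directly from Table 5 when the other lesions are unchanged.

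Only secondary descriptive endpoints are affected. DLT assessment, the MTD decision and the sample size are not. The change to response scoring is worth making before response data accumulate. Censoring PFS or duration of response as the main analysis is not supported.

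**What to change.** Leave 4.1.1 as it stands. In 6.3.5 and 8.4.3.1, add:

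- After local therapy to a target lesion, later assessments cannot count toward CR, PR or SD for best response or disease control. Status reached before that date is kept, and the subject stays in the denominator.
- PD in untreated or new lesions still counts after local therapy.
- A non-target lesion treated locally cannot contribute to CR.

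Record the date and site of any local therapy on the CRF, and report the number of subjects who had it. A count needs no individual tabulation, so it fits 8.4.8.

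Keep the definitions of PFS and duration of response, adding that PD is also judged on the untreated lesions after local therapy. Show censoring at local therapy only as a sensitivity analysis, with the note that it may be informative.

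The cost is a few lines of text and one CRF entry. The downside is that later response assessments of the few locally treated subjects are lost, including any genuine later response in their untreated lesions, and ORR and DCR may be slightly lower.
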